7.3.2 Handling of Expedited Safety Reports

In accordance with local regulations, BMS will notify investigators of all SAEs that are suspected (certainly, probably, or possibly related to the investigational product) and unexpected (ie, not previously described in the Investigator Brochure). In the European Union (EU), an event meeting these criteria is termed a Suspected, Unexpected Serious Adverse Reaction (SUSAR). Investigator notification of these events will be in the form of an expedited safety report (ESR).

Other important findings which may be reported by the sponsor as an ESR include: increased frequency of a clinically significant expected SAE, an SAE considered associated with study procedures that could modify the conduct of the study, lack of

efficacy that poses significant hazard to study subjects, clinically significant safety finding from a nonclinical (eg, animal) study, important safety recommendations from a study data monitoring committee, or sponsor decision to end or temporarily halt a clinical study for safety reasons.

Upon receiving an ESR from BMS, the investigator must review and retain the ESR with the Investigator Brochure. Where required by local regulations or when there is a central IRB/IEC for the study, the sponsor will submit the ESR to the appropriate IRB/IEC. The investigator and IRB/IEC will determine if the informed consent requires revision. The investigator should also comply with the IRB/IEC procedures for reporting any other safety information.

In addition, suspected serious adverse reactions (whether expected or unexpected) shall be reported by BMS to the relevant competent health authorities in all concerned countries according to local regulations (either as expedited and/or in aggregate reports).

7.3.3 Nonserious Adverse Events

The collection of nonserious AE information should begin at initiation of investigational product. Nonserious AE information should also be collected from the start of a placebo lead-in period or other observational period intended to establish a baseline status for the subjects.

If an ongoing nonserious AE worsens in its intensity, or if its relationship to the investigational product changes, a new nonserious AE entry for the event should be completed. Nonserious AEs should be followed to resolution or stabilization, or reported as SAEs if they become serious. Follow-up is also required for nonserious AEs that cause interruption or discontinuation of investigational product, or those that are present at the end of study participation. Subjects with nonserious AEs at study completion should receive post-treatment follow-up as appropriate.

All identified nonserious AEs must be recorded and described in the medical record.

7.3.4 Pregnancy

All participants will be male. If a female partner becomes pregnant during the research study, the female partner will be asked to sign a consent to follow the pregnancy for outcomes and any possible side effects from the study drug.

7.3.5 Other Safety Considerations

Any significant worsening noted during interim or final physical examinations, electrocardiograms, x-rays, and any other potential safety assessments, whether or not these procedures are required by the protocol, should also be recorded in the medical record

8 STATISTICAL METHODOLOGY

8.1 Study Design

This is a single arm phase II trial.

8.2 Primary and Secondary Endpoints

The primary endpoint is the achievement of an undetectable PSA defined as $PSA \le 0.2$ ng/mg after initiation of ipilimumab therapy. The secondary endpoints are: time to PSA progression, time to disease progression by any measure, time to death from any cause, number of patients with immune related Adverse Events (IRAEs), correlation between IRAEs and clinical outcomes, and the ratio of T regulatory cells to T effector cells, and additional measures of immune responses.

8.3 Sample Size Justification

N=30 (for the final analysis, 10 for the intial analysis). Using the Simon two-stage design for Phase II trials, the initial accrual will be 10 patients. Assuming that 10% of patients receiving usual care will achieve an undetectable PSA (PSA \leq 0.2) without additional intervention, the trial has a 80% power to detect a rate of achieving an undetectable PSA of \geq 30% among patients treated with ipilimumab. At least two patients with an undetectable PSA will be required in the first 10 patients to continue to stage 2. As soon as two patients having achieved an undectable PSA are identified, stage 2 for of the study will begin. If 6 or more of 30 patients have achieved an undetectable PSA at 6 months, the study will be considered successful and the regimen worthy of further investigation. This design has a type I error rate of 0.05 and a type II error rate of 0.20.

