N=30 (for the final analysis, 10 for the intial analysis). Using the Simon two-stage design for Phase II trials, the initial accrual will be 10 patients. Assuming that 10% of patients receiving usual care will achieve an undetectable PSA without additional intervention, the trial has a 80% power to detect a rate of achieving an undetectable PSA of \geq 30% among patients treated with ipilimumab. At least two patients with an undetectable PSA will be required in the first 10 patients to continue to stage 2. As soon as two patients achieve an undectable PSA, stage 2 for of the study will begin. If 6 or more of 30 patients have achieved an undetectable PSA at 6 months, the study will be considered successful and the regimen worthy of further investigation. This design has a type I error rate of 0.05 and a type II error rate of 0.20.

Demographic and clinical characteristics will be summarized using descriptive statistics (e.g. proportions, mean, standard deviation, median, range). The proportion of patients who achieve an undetectable PSA (≤0.2 ng/ml) after initiation of ipilimumab therapy will be provided with the exact 95% confidence interval. The Kaplan-Meier method will be used to estimate time to PSA progression, time to disease progression by any measure and time to death from any cause. In evaluation of time to PSA progression and time to disease progression by any measure will be censored for: (1) lost to follow-up at the date of last contact, (2) use of additional cancer therapies that would interfere with ascertainment of the endpoint of interest (3) death from causes other than prostate cancer or treatment of prostate cancer. Evaluation of time to death will be censored for lost to follow-up at last contact.

The effects of IRAEs and other immune parameters (e.g., a ratio of T regulatory cells to T effector cells) on clinical outcomes will be evaluated using logistic regression for binary endpoints (e.g., achievement of undetectable PSA) and Cox regression for the time to event outcomes (e.g., time to PSA progression).

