2 STUDY OBJECTIVES

2.1 Primary Objective

Proportion of patients who achieve an undetectable PSA (≤ 0.2 ng/ml) after initiation of Ipilimumab therapy.

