3.6 Follow-up visits after completion of ipilimumab therapy

Patients will be followed with a history, physical exam, CT and NM bone scan and serum PSA quarterly along with treatment visits during the maintenance treatment phase, until radiographic progression. If a patient has not met radiographic progression by Week 60 visit, the patient will be followed by PSA and scans until radiographic progression. Following radiographic progression, patients will be followed by semi-annual phone surveys with the patient, his family, or his treating physician to collect data on treatment status and overall survival for up to 5 years after all protocol treatment has been completed.

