6.4.2 Efficacy Evaluation

The **primary endpoint** is fraction of patients who achieve an undetectable PSA (≤ 0.2 ng/ml). Pursuant to that endpoint, we will check the PSA every 3 weeks during the first 4 cycles and every 6 weeks during weeks 12-24, then every three months as the patient is being followed (planned follow up through year 5).

The **secondary endpoints** explore the objective responses achieved in the realm of non-progression of disease and tumor regression, as well as provide an opportunity to learn more about the immune response itself. Part of this assessment is PSA-based and part is based on radiographs (bone scans and CT scans). We will use the procedures described for the primary endpoint, above, to look at response endpoints. Additionally, a CT scan of the chest/abdomen/pelvis and bone scan at baseline, week 12, week 24 and every 6 months thereafter will be done for comparison. We will also perform a history and physical prior each cycle to detect new pain that could indicate cancer progression. After the 8 cycles of ipilimumab, patients will have their PSA checked every 3 months, either at the study center or by an outside provider. Their survival status will be assessed by telephone survey every 6 months for a maximum of 5 years. For the correlative work, we will collect blood samples prior to each infusion of ipilimumab and quantify the immune response. Once the study is complete, we will compare the objective response with the depth of the immune response.

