8.5 Statistical Analysis Plan

Demographic and clinical characteristics will be summarized using descriptive statistics (e.g. proportions, mean, standard deviation, median, range). The proportion of patients who achieve an undetectable PSA (≤ 0.2 ng/ml) after initiation of ipilimumab therapy will be provided with the exact 95% confidence interval. The Kaplan-Meier method will be used to estimate time to PSA progression, time to disease progression by any measure and time to death from any cause. In evaluation of time to PSA progression and time to disease progression by any measure will be censored for:

- 1) lost to follow-up at the date of last contact
- 2) use of additional cancer therapies that would interfere with ascertainment of the endpoint of interest
- death from a causes other than prostate cancer or treatment of prostate cancer.

Evaluation of time to death will be censored for lost to follow-up at last contact.

The effects of IRAEs and other immune parameters (e.g., a ratio of T regulatory cells to T effector cells) on clinical outcomes will be evaluated using logistic regression for binary endpoints (e.g., achievement of undetectable PSA) and Cox regression for the time to event outcomes (e.g., time to PSA progression).

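### The primary endpoint has no single time window: the 6-of-30 success rule is dated at 6 months, but the stage 1 rule, the 10% and 30% rates and the reported proportion have no end date

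*Combined protocol and SAP*

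**What the plan says.** One sentence puts a date on the primary endpoint. Section 8.3 states: "If 6 or more of 30 patients have achieved an undetectable PSA at 6 months, the study will be considered successful". The Statistics part of the synopsis repeats the condition: "If 6 or more of 30 patients have achieved an undetectable PSA at 6 months".

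The other statements of the endpoint have a start but no end, or no time at all:

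- Section 2.1 counts patients who reach the threshold "after initiation of Ipilimumab therapy".
- Section 8.2 ("The primary endpoint is the achievement of an undetectable PSA defined as" a PSA at or below 0.2) also starts at the first dose and gives no end.
- Section 8.3 attaches no time to the 10% usual-care rate, the 30% target rate or the requirement of at least two responders among the first 10. Stage 2 is triggered by identification alone: "As soon as two patients having achieved an undectable PSA are identified, stage 2 for of the study will begin".
- Section 8.5 plans the estimate on the open definition: the proportion "after initiation of ipilimumab therapy will be provided with the exact 95% confidence interval".
- Section 6.4.2.1 describes the endpoint as measured on study.

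PSA measurement does not stop at month 6. Section 6.4.2 presents its PSA schedule as serving the primary endpoint and continues it past Week 24: "then every three months as the patient is being followed (planned follow up through year 5". Section 3.6 says that without radiographic progression by Week 60 "the patient will be followed by PSA and scans until radiographic progression", and footnote 4 of the Time and Events Schedule also runs PSA to radiographic progression. The schedule has PSA draws at Wk 23/24, Wk 24, Wk 36, Wk 48 and Wk 60.

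**The concern.** A two-stage design has the error rates claimed for it only if the interim rule, the final rule and the two rates count the same event. Here they need not. A patient whose PSA first reaches the threshold at Week 36 is a responder for stage 1 and for the estimate in 8.5, but not for the 6-of-30 rule.

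Three things follow from the text:

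1. Stage 2 can open on responses that cannot contribute to success.
2. Having fewer than two responders among 10 is never final while any of those patients still has PSA draws due, so the futility stop has no closing date.
3. The trial can fail its success rule while the reported primary proportion is 6 of 30 or more, leaving two primary results.

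Late first responses are possible on the plan's own account. Section 6.4.4 expects immune activation to take weeks to months, and patients without progression are given further doses from Week 24 to Week 60.

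**Working it through.** **Inputs from 8.3.** Stage 1 n = 10, continue with at least 2 responders; stage 2 adds 20; success with at least 6 of 30; rates 10% and 30%; stated type I error 0.05 and power 80%.

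**Step 1: reproduce the design with a single window.** With response rate p,

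P(success) = Σ (x = 2 to 10) Bin(x; 10, p) × P(Bin(20, p) ≥ 6 − x).

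- p = 0.10: 0.0525 (stated 0.05).
- p = 0.30: 0.8146 (stated 0.80).
- Early stopping at p = 0.10: P(Bin(10, 0.10) ≤ 1) = 0.3487 + 0.3874 = 0.7361.
- Expected N at p = 0.10: 10 + 20 × (1 − 0.7361) = 15.3.

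The stated power reproduces and the type I error is close to the stated value.

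**Step 2: separate the windows.** Let *a* be the probability of responding by 6 months and *b* the probability of responding at any time, so *b* − *a* is the probability of a late-only response. In stage 1 let x be the six-month responders and y the late-only responders. If stage 1 counts any response and success counts only those by 6 months,

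P(success) = Σ over x + y ≥ 2 of Multinomial(x, y, 10 − x − y; *a*, *b* − *a*, 1 − *b*) × P(Bin(20, *a*) ≥ 6 − x).

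Early stopping is P(Bin(10, *b*) ≤ 1), and expected N is 10 + 20 × (1 − that probability). The documents give no *a* and *b* separately, so every pair below is an assumption.

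**Step 3: null, both readings of the 10%, stage 1 open-ended.**

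| Reading | *a* | *b* | Early stopping | Expected N | Type I error |
|---|---|---|---|---|---|
| One window | 10% | 10% | 73.6% | 15.3 | 5.3% |
| 10% is the six-month null | 10% | 12% | 65.8% | 16.8 | 5.6% |
| 10% is the six-month null | 10% | 15% | 54.4% | 19.1 | 6.0% |
| 10% is the any-time null | 8% | 10% | 73.6% | 15.3 | 2.2% |

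**Step 4: decision and reported count disagree.** This is the summed probability that stage 1 is passed, the six-month count is 5 or fewer and the any-time count is 6 or more of 30. With *a* = 10% and *b* = 12% or 15% it is 4.9% or 15.7% when stage 1 is open-ended, and 3.4% or 8.6% when stage 1 counts only six-month responders.

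**Step 5: power, both readings of the 30%, stage 1 open-ended.**

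| Reading | *a* | *b* | Power |
|---|---|---|---|
| One window | 30% | 30% | 81.5% |
| 30% is the six-month rate | 30% | 36% | 86.9% |
| 30% is the any-time rate | 28% | 30% | 78.7% |
| 30% is the any-time rate | 25% | 30% | 72.0% |

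**Step 6: the undated stop.** With a Week 24 cut-off, stage 1 can be settled 24 weeks after the tenth patient starts. Without one, if fewer than two have responded and one of the ten has not progressed, it can still be open at Week 60: 60 − 24 = 36 more weeks.

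**The case against.** The strongest reply is that 6 months is the only time point in 8.3, so a sensible team would apply it to the whole paragraph and close stage 1 there. The trigger for stage 2 also means that no wait arises when two patients respond early. Both points limit how often the problem would occur: Week 60 is a worst case, not the expected course. They do not remove it. No section extends the 6 months to the endpoint, and 6.4.2 and 6.4.2.1 point the other way. The other 6-month assessment, in 6.4.3.3, concerns tumor response.

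A second reply stands in full: the loss of early stopping depends on reading 10% as a six-month rate. Read as an any-time rate, 10% gives unchanged early stopping and a conservative type I error.

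A reader might be tempted to go further in three ways that the documents do not support:

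- That type I error is badly inflated. This would need late responses to count toward 6 of 30, and the written rule dates that count at 6 months.
- That the 80% power is wrong. It reproduces when 30% is the six-month rate and falls short only if 30% is an any-time rate with some responses coming late. The text does not say which it is.
- That the exact interval for a late 6 of 30 settles whether the decision would change. The rule is a count, not an interval, so the interval has no bearing on it.

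**Conclusion.** The point stands as a conflict between stated rules. The plan dates the decision and leaves the interim rule, the rates and the reported estimate undated, so the three can rest on different responder sets and futility has no declared date. That conclusion needs no assumed rate.

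The numerical size does. It runs from no loss of early stopping (any-time null of 10%) to a drop of about 19 points (73.6% to 54.4%, six-month null of 10% with 15% at any time), and from power at or above 81.5% to power of 72.0%. Type I error stays between 2.2% and 6.0% across the cases shown. These cases treat the success rule as counting responses by 6 months. Whether the PSA must instead be undetectable at that assessment is also unstated.

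This should be fixed, because otherwise the choice of which responders count could be made after the PSA results are known.

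**What to change.** Apply one window, closing at the 6-month (Week 24) PSA assessment that the success rule already implies:

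- Use it in the responder definition in the synopsis, 2.1, 6.4.2, 8.2, 8.3 and 8.5, and state in 8.3 that the 10% and 30% rates refer to it.
- For stage 1, open stage 2 at the second response within the window among the first 10. Declare futility if there are fewer than two once all 10 have passed that assessment or left PSA follow-up.
- Use the same responders for the 6-of-30 rule and for the proportion with its exact interval.
- Count patients with no qualifying PSA as non-responders, so that the proviso in 8.4 about measured endpoints does not shrink the denominator.
- Report responses first seen after the window as a secondary endpoint.

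Three choices belong to the sponsor and should be stated: whether one value by that assessment is enough or the value at it must be undetectable; whether confirmation is required; and whether the Wk 23/24 or the Wk 24 draw closes the window.

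Cost: all draws are already scheduled, and with a single window the design keeps its type I error of 5.3% and power of 81.5%. The study is open, so this is a protocol amendment. It should be made, and recorded as made, without reference to accumulated PSA results. The drawback is that responses first seen during maintenance no longer count toward the primary endpoint.

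Two separate points can be reconciled in the same amendment but do not support this one: 6.4.2.1 uses below 0.2 where other sections use at or below 0.2, and the end of PSA follow-up differs between 6.4.2 and 3.6 with schedule footnote 4.

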8.4 Analysis Populations

An Intention to Treat (ITT) population includes all patients who sign the consent and are assigned to a treatment regardless of the actual drug dose the patients receive. Safety analysis population includes all patients who receive at least one drug dose. Per Protocol

Population includes those who receive the prescribed dose of the drug per protocol and excludes patients who drop out of the study prematurely. Whenever possible, we will use the ITT population to analyze the primary and secondary endpoints provided that their primary and secondary endpoints are measured. As a secondary analysis, per protocol population will be used for the analysis of the primary and secondary endpoints. Safety analysis population will be used to analyze safety and toxicity data.

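### Should section 8.3 print attained error rates of 0.0525 and 0.185 instead of 0.05 and 0.20?

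*Combined protocol and SAP*

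**What the plan says.** Section 8.3 (Sample Size Justification) and the Statistics entry of the synopsis give every input to the design.

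- Null rate: "Assuming that 10% of patients receiving usual care will achieve an undetectable PSA".
- Target rate and power: "the trial has a 80% power to detect a rate of achieving an undetectable PSA" of at least "30% among patients treated with ipilimumab".
- Interim rule: "At least two patients with an undetectable PSA will be required in the first 10 patients to continue to stage 2".
- Final rule: "If 6 or more of 30 patients have achieved an undetectable PSA at 6 months, the study will be considered successful".
- Error rates: "This design has a type I error rate of 0.05 and a type II error rate of 0.20".

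The design is called a Simon two-stage design, with neither the optimal nor the minimax variant named. The error rates are not labelled as nominal or as attained. Section 8.4 analyses the endpoints in the ITT population, "provided that their primary and secondary endpoints are measured".

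**The concern.** The sentence on error rates is worded as a property of the design, and a reader who enumerates the written rule does not get that pair. The attained type I error lies slightly above 0.05, which matters if 0.05 is meant as a ceiling. The attained type II error rounds to 0.19 and not to 0.20.

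The figures also presuppose 30 patients, while section 8.4 allows patients without a measured endpoint to be left out. With fewer measured patients and unchanged cut-offs, both error rates move. If the type I error were materially above its stated level, or the power materially below it, the claim that a positive result makes the regimen worth pursuing would rest on weaker evidence than the protocol says.

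**Working it through.** **Inputs (section 8.3).** p0 = 0.10, p1 = 0.30; 10 patients in stage 1 and 30 in total, so 20 in stage 2; continue if X1 ≥ 2; success if X1 + X2 ≥ 6.

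**Formula.** With X1 ~ Bin(10, p) and X2 ~ Bin(20, p) independent, the probability of declaring success is

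Σ (x = 2 to 10) P(X1 = x) · P(X2 ≥ 6 − x),

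where the second factor is 1 once x ≥ 6. At p0 this is the type I error, one-sided by construction; at p1 it is the power.

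**Results for the rule as written.**

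| Stage 1 successes x | p = 0.10: P(X1 = x) × P(X2 ≥ 6 − x) | p = 0.30: P(X1 = x) × P(X2 ≥ 6 − x) |
|---|---|---|
| 2 | 0.19371 × 0.13295 = 0.02575 | 0.23347 × 0.89291 = 0.20847 |
| 3 | 0.05740 × 0.32307 = 0.01854 | 0.26683 × 0.96452 = 0.25736 |
| 4 | 0.01116 × 0.60825 = 0.00679 | 0.20012 × 0.99236 = 0.19859 |
| 5 | 0.00149 × 0.87842 = 0.00131 | 0.10292 × 0.99920 = 0.10284 |
| 6 or more | 0.00015 × 1 = 0.00015 | 0.04735 × 1 = 0.04735 |
| Sum | 0.0525 | 0.8146 |

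The unrounded totals are 0.05254 and 0.81461.

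- Type I error: 0.0525 against 0.05 stated. The excess is 0.05254 − 0.05 = 0.00254, or 1/394.
- Power: 0.8146 against 0.80 stated.
- Type II error: 1 − 0.8146 = 0.1854 against 0.20 stated.

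**Where the printed pair may come from.** A search over Simon designs with type I error at most 0.05 and power at least 0.80 gives, as the optimal design, at least 2 of 10 and then at least 6 of 29. Its type I error is 0.0471, its power 0.8051 and its type II error 0.1949. These round to 0.05 and 0.20. The plan may be this design with one patient added, but the document does not say so. The pair is equally the conventional set of design targets.

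**Patients without a measured PSA, cut-offs unchanged.** Here p0 and p1 are taken as rates among measured patients.

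| Measured patients | Type I error | Power |
|---|---|---|
| 30 | 0.053 | 0.815 |
| 29 (one stage 2 patient missing) | 0.047 | 0.805 |
| 28 (two stage 2 patients missing) | 0.042 | 0.793 |
| 27 (three stage 2 patients missing) | 0.037 | 0.779 |
| 29 (one stage 1 patient missing) | 0.043 | 0.765 |

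The rule counts successes against fixed thresholds. An unmeasured patient adds nothing to the count whether he is excluded or scored as a failure, so the decision, and each line of this table, is the same under both conventions. Fixing the denominator at 30 therefore would not secure 0.0525 and 0.815; having 30 measured patients would.

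**The case for a change.** The strongest case for an edit is that no single reading makes both printed numbers right for 30 patients. Read as attained values, the type I error matches after rounding but the type II error does not (0.19 against 0.20). Read as limits, the type II error is met but the type I error is exceeded. The edit would be wording only, and stating the denominator would tie the rule to the figures.

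The arithmetic in this argument stands; the need for a correction does not follow. The departure from the limit is 0.0025, below the precision at which the rate is printed, and the departure on the type II error is in the trial's favour.

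The denominator part fails. Section 8.3 already writes the final rule out of 30 patients, and scoring unmeasured patients as failures leaves the decision unchanged. What section 8.4 leaves open about missing PSA values is a separate matter from whether 0.05 and 0.20 are acceptable figures. The table does show power below 80% after two stage 2 losses or one stage 1 loss, but reprinting the error rates would not prevent that.

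Printing a third decimal as exact would also carry an assumption the plan does not state. Section 8.3 attaches the 6-month time point to the final rule only, so the enumeration is exact only if the same endpoint definition applies at the interim look.

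**Conclusion.** No change follows. For the rule as written, the attained one-sided type I error is 0.0525, which is 0.05 at the printed precision, and the power is 0.815, which meets the stated 80%. The stated type II error of 0.20 is conservative against 0.185. Replacing conventional design rates with attained ones would alter no cut-off, sample size, decision or conclusion, and the gap shows no failure of error control. Any reader can derive the exact values from the inputs printed in section 8.3.

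This rests on all 30 patients having a measured PSA, independent outcomes at the stated 10% and 30%, the same endpoint definition at both stages, and the first 10 patients staying in the final count. Under that last condition, opening stage 2 as soon as two successes are seen leaves the rates unchanged.
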